Chronic eosinophilic rhinosinusitis	Infusion site hypersensitivity	Rhinitis allergic	
Chronic hyperplastic eosinophilic sinusitis	Infusion site rash	Scleral oedema	
Circulatory collapse	Infusion site recall reaction	Scleritis allergic	
Circumoral oedema	Infusion site urticaria	Scrotal dermatitis	
Circumoral swelling	Infusion site vasculitis	Scrotal oedema	
Conjunctival oedema	Injection related reaction	Serum sickness	
Conjunctivitis allergic	Injection site dermatitis	Serum sickness-like reaction	
Contact stomatitis	Injection site eczema	Shock	
Contrast media allergy	Injection site hypersensitivity	Shock symptom	
Contrast media reaction	Injection site rash	Sinus bradycardia	
Corneal oedema	Injection site recall reaction	SJS-TEN overlap	

37) COVID-19 vaccines include the following preferred term codes (WHODrug BMAR2022):

Prohibited PREF Codes	Prohibited PREF Codes	Prohibited PREF Codes
00002001001	15268629001	15268666001
06201402001	15268630001	15268667001
06439204001	15268631001	15268668001
06559301001	15268632001	15268669001
06559307001	15268633001	15268670001
13195801001	15268634001	15268671001
13949502001	15268635001	15268672001
13950013001	15268636001	15268673001

Prohibited PREF Codes	Prohibited PREF Codes	Prohibited PREF Codes
14953401001	15268637001	15268674001
14953501001	15268638001	15268675001
15092101001	15268639001	15268676001
15268601001	15268640001	15268677001
15268602001	15268641001	15268678001
15268603001	15268642001	15268679001
15268604001	15268643001	15268680001
15268605001	15268644001	15268681001
15268607001	15268645001	15268682001
15268609001	15268646001	15268683001
15268610001	15268647001	15268684001
15268611001	15268648001	15268685001
15268612001	15268649001	15268686001
15268613001	15268650001	15268687001
15268614001	15268651001	15268688001
15268615001	15268652001	15268689001
15268616001	15268653001	15268690001
15268617001	15268654001	15268691001
15268618001	15268655001	15268692001
15268619001	15268656001	15268693001
15268620001	15268657001	90031301001
15268621001	15268658001	
15268622001	15268659001	
15268623001	15268660001	
15268624001	15268661001	
15268625001	15268662001	
15268626001	15268663001	
15268627001	15268664001	
15268628001	15268665001	

38) Antithrombotic medications include the following drugs:

Drug name
Direct factor Xa inhibitors
Direct thrombin inhibitors
Low molecular weight heparins (LMWH) and heparinoids
Other heparins
Other antithrombotic drugs
Platelet aggregation inhibitors, excluding heparin
Thrombolytic drugs
Vitamin K antagonists
Heparins

with preferred term codes (WHODrug BMAR2022):

Prohibited PREF Codes	Prohibited PREF Codes	Prohibited PREF Codes	Prohibited PREF Codes	Prohibited PREF Codes	Prohibited PREF Codes	Prohibited PREF Codes
06259501001	13765501001	12384902001	12353501001	13595102001	11890502001	12800601001
06324201001	13765502001	13825101001	12353502001	11902101001	12829002001	11012901001
06324202001	13766301001	13825102001	12354601001	11902102001	12779502001	13576201001
06297801001	15159701001	13824801001	12354201001	12382602001	12779503001	11885501001
06297802001	15159702001	12385301001	12354202001	12382402001	12779602001	13576701001
06297803001	12430501001	12385501001	12353602001	12382601001	11485302001	90045701001
01551201001	12430502001	12384901001	12353601001	12382401001	11756602001	13185301001
01551202001	11096401001	13824501001	13623001001	12382403001	12150301001	12189002001
05705201001	11096402001	11549402001	12150502001	13749001001	11923801001	12189003001
01369401001	11902001001	11549401001	12150503001	13707401001	12151101001	12189001001
01369402001	11902002001	10534502001	12150501001	13707402001	11902401001	13599601001
01506801001	13600801001	10534501001	11610504001	11890503001	11641801001	13599602001
01506802001	12150602001	12268601001	11610502001	12406404001	13629501001	11442802001
01633201001	12150601001	12268602001	11610002001	12406403001	12150201001	11442801001
01633202001	01384201001	12269902001	11610203001	12382702001	11492701001	12180302001
01633203001	01384202001	12283302001	11610202001	11578403001	13313701001	12646902001
01288601001	11097102001	11177702001	14527702001	11578402001	12151401001	12646901001
01346001001	11678602001	12283301001	12406402001	11096101001	10907301001	00889601001
01384201001	11678601001	12269901001	12456903001	11096102001	11052701001	00889603001
01384202001	11097101001	11177701001	12456902001	12416702001	12286502001	00889602001
07368201001	13431901001	14427201001	12156601001	12416701001	12286501001	11866102001
07368202001	11623502001	14421501001	12156602001	00027701001	13572501001	11866101001
01708301001	11623501001	14488101001	11699802001	00027702001	12150701001	00723702001

Prohibited PREF Codes	Prohibited PREF Codes	Prohibited PREF Codes	Prohibited PREF Codes	Prohibited PREF Codes	Prohibited PREF Codes	Prohibited PREF Codes
01708302001	13629801001	14488102001	11699803001	90006801001	12408701001	12344202001
01353901001	12181303001	01691801001	12186802001	00027705001	12406401001	11643102001
01353902001	12181302001	11699701001	11699602001	00027711001	12457201001	11012902001
06297801001	12181301001	11699702001	11699801001	00027710001	12456901001	13576202001
06297802001	07368201001	12475602001	12186801001	00027704001	12690401001	11885502001
06297803001	07368202001	12475601001	11699601001	00027708001	10999501001	01437701001
01707901001	12472001001	11375501001	14440702001	00027712001	12150901001	01437702001
01707902001	12472002001	11375502001	14440701001	00027707001	12382701001	07957701001
07957501001	11645802001	15876401001	01708201001	12150302001	12151201001	07957702001
07957502001	11645801001	15260602001	01708202001	11923802001	15778101001	00552101001
10679802001	10995602001	15260601001	12231802001	12151102001	12748001001	00552102001
13575901001	10995601001	12424001001	12231801001	11902402001	12517101001	11196102001
13575902001	12747502001	12424002001	11095802001	11641802001	11890501001	11657802001
10679801001	12747501001	10685602001	11095801001	13629502001	12829001001	11173402001
12601302001	12471001001	10685601001	11610503001	12150202001	14455101001	11196101001
12150802001	12471002001	01708301001	13472301001	11492702001	12779501001	11657801001
12150801001	11645702001	01708302001	13472302001	12151402001	12779601001	11173401001
12669701001	11645701001	01353901001	11718202001	10907302001	11485301001	13178201001
12669702001	11729402001	01353902001	11718201001	10907303001	15876301001	05509001001
11681801001	11729401001	07957801001	11610501001	11052702001	15878201001	05509002001
11681802001	12385504001	07957802001	11610001001	12150702001	11756601001	08069601001
12601301001	12385602001	07368001001	11610201001	12408702001	00723701001	08069602001
12430802001	12385601001	12190302001	14527701001	12457202001	13599501001	07579101001
13802202001	12385002001	12190301001	12382902001	12690402001	13720001001	07579102001
12431002001	12385001001	11514301001	12382302001	10999502001	13313601001	08336301001
12431001001	12479901001	11514302001	11885902001	12150902001	12180301001	01486301001
12430801001	12479902001	11732402001	12382301001	12151202001	12188202001	01063701001
13802201001	12385502001	11732301001	12382901001	12748002001	12188201001	00027709001
13802203001	12385503001	11732302001	11885901001	12748003001	12344201001	06563401001
15767701001	12385302001	11732401001	13595301001	12517103001	11643101001	06563402001

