All other untoward medical occurrences observed during the screening period, including exacerbation or changes in medical history, are to be considered medical history. See Section 7, Adverse Events and Toxicity Management, for additional details.

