7.7. Toxicity Management

Infusion-related reactions have been observed during and following administration of RDV. Signs and symptoms may include hypotension, hypertension, tachycardia, bradycardia, hypoxia, fever, dyspnea, wheezing, angioedema, rash, nausea, diaphoresis, and shivering. Slower infusion rates, with a maximum infusion time of up to 120 minutes, can be considered to potentially prevent these signs and symptoms. If signs and symptoms of a severe infusion-related reaction occur, immediately discontinue administration of RDV and initiate appropriate treatment. Remdesivir infusions will be administered to participants at the site under close supervision. Healthcare professionals administering RDV infusions must have the appropriate medication available for immediate use in case of hypersensitivity or infusion-related reactions. The participant should be treated according to the SOC for management of hypersensitivity reaction or infusion-related reactions. Participants should be monitored for at least 2 hours after the RDV infusion is completed.

All clinical events and clinically significant laboratory toxicities will be managed according to uniform guidelines detailed in [Appendix 6](#), and as outlined below.

Grade 3 or 4 clinically significant laboratory abnormalities that were not present at baseline should be confirmed by repeat testing as soon as possible, and preferably within 3 calendar days after receipt of the original test results.

The Gilead medical monitor should be consulted prior to investigational drug discontinuation when medically feasible.

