7.1.5. Treatment-Emergent Adverse Events

7.1.5.1. Definition of Treatment-Emergent Adverse Events

Treatment-emergent adverse events (TEAEs) are defined as 1 or both of the following:

- Any AEs with an onset date on or after the study drug start date and no later than 30 days after permanent discontinuation of study drug
- Any AEs leading to premature discontinuation of study drug.

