Appendix 2. Programming Specifications

- 1) If the age from the Day 1 eCRF is not available, age will be calculated as follows:

Only year is provided for the date of birth (DOB). Use July 1 for the month and day.

- a) AGE (years) is calculated from the number of days between the DOB and Study Day 1,
- b) Use the SAS INTCK function to determine the number of “1st-of-month days” (eg, January 1st, February 1st, March 1st) between DOB and Day 1 (inclusive),
- c) Divide the result in (b) by 12,

AGE = the integer of the result in (c),

Age for laboratory test reference range will be based on the age at the sample collection date.

- 2) All screened participants refer to all participants who are screened (ie, with non-missing screening date) and have a screening number. For summaries the same participant is counted only once.
- 3) Screen failure participants are the participants who were screened and answered “No” for any inclusion criteria or “Yes” for any exclusion criteria regardless of which version of protocol the participant was consent to.
- 4) Participants in the randomized analysis set are defined as participants randomized into the study. IXRSRAND is the source to determine whether the participant is randomized (ie, participant with non-missing RGMNDTN in the IXRSRAND dataset), and confirmed by the eCRF ENROLL dataset (ie, ENROLLYN = “Yes” in ENROLL dataset).
- 5) Randomized treatment (ie, TRT01P in ADSL) is derived from IXRSRAND, while actual treatment received (ie, TRT01A in ADSL) is assigned as the randomized treatment if participant took at least 1 dose of study drug and assigned as blank if the participant was never dosed.
- 6) In the disposition table, the reasons for premature discontinuation are displayed in the order as they appear on the eCRF.

- 7) Body mass index (BMI)

BMI will be calculated only at baseline as follows:

$$\text{— BMI} = (\text{weight [kg]}) / (\text{height [meters]}^2)$$

Baseline height and weight will be used for this calculation if available

8) TEAE

Events with Missing Onset Day and/or Month

An event is considered treatment emergent if all of the following 3 criteria are met:

- i. The month and year (or year) of onset date is the same as or after the month and year (or year) of the first dose of study drug, and
- ii. The month and year (or year) of the onset date is the same as or before the month and year (or year) of the 30th day after the date of the last dose of study drug, and

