- iii. End date is as follows:

The (complete) end date is on or after the first dose date, or

The month and year (or year) of end date is the same or after the month and year (or year) of the first dose of study drug, or

End date is completely missing

Events with Completely Missing Onset Date

An AE with a completely missing onset date is defined as TEAE if end date meets any of the 3 criteria specified above.

9) Baseline risk factor

Selected medical history will be summarized as baseline risk factor and be included as subgroups in analysis. The risk factor of “current cancer” for a participant is defined as a medical history of one of these diseases:

- At least 1 ongoing medical history record with MedDRA PT (mh.MDRPT) in the following selected PT listing for the corresponding disease with start date on or prior to the first dose date;
- At least 1 ongoing AE record with MedDRA PT (ae.MDRPT) in the following selected PT listing for the corresponding disease with start date on or prior to the first dose date.

Other risk factors for a participant is defined as a medical history of one of these diseases:

- At least 1 medical history record with MedDRA PT (mh.MDRPT) in the following selected PT listing for the corresponding disease with start date on or prior to the first dose date;
- At least 1 AE record with MedDRA PT (ae.MDRPT) in the following selected PT listing for the corresponding disease with start date on or prior to the first dose date. If the start date is incomplete but the month and year (or year alone) of the start date is the same as or before the month and year (or year alone) of the first dosing date of study drug, the event will be included. If the start date is completely missing, the event will be included.

If the ongoing status is missing for an event:

- If the end date is completely missing and start date is the same as or before the first dosing date of the study drug, the event will be included;
- If the end date is completely missing and start date is after the first dosing date of the study drug, the event will not be included;
- If the end date is incomplete but the month and year (or year alone) of the end date is the same as or after the month and year (or year alone) of the first dosing date of study drug, the event will be included;

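### Baseline risk-factor subgroups can be filled by adverse events that began after the first dose

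*SAP*

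**What the plan says.** SAP 3.4 lists seven yes/no baseline risk factors as subgroups for the primary endpoint and for all-cause mortality: chronic lung disease, hypertension, cardiovascular or cerebrovascular disease, diabetes, immunocompromised state, chronic liver disease and current cancer. SAP 5.2 tabulates the same factors by arm, with a test between arms.

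SAP Appendix 2 item 9 derives each factor from medical history or from AE records. For the six factors other than current cancer, an AE record qualifies in three ways:

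- (a) Fully dated record: "At least 1 AE record with MedDRA PT (ae.MDRPT) in the following selected PT listing for the corresponding disease with start date on or prior" (the cut-off being the day of first dosing).
- (b) Partly dated record: it counts when, judged by month and year or by year alone, "the start date is the same as or before the month and year (or year alone) of the first dosing date of study drug".
- (c) Undated record: "If the start date is completely missing, the event will be included".

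Current cancer has its own bullets. They require an ongoing record and carry condition (a), but not (b) or (c).

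The treatment-emergent rules are in SAP 7.1.5 and Appendix 2 item 8. They take in "Any AEs with an onset date on or after the study drug start date" (up to 30 days after stopping drug). For partial dates, the condition is "The month and year (or year) of onset date is the same as or after the month and year (or year) of the first" (that is, first dosing). For missing dates, "An AE with a completely missing onset date is defined as TEAE if end date meets any of the 3 criteria specified above".

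On what is recorded before dosing, Protocol 7.3.1 puts only SAEs and procedure-related AEs on the AE form. For the rest, Protocol 6.2.1 says: "All other untoward medical occurrences observed during the screening period, including exacerbation or changes in medical history, are to be considered medical history". After dosing, Protocol 7.3.2 collects all AEs.

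**The concern.** A baseline subgroup should be fixed before treatment can influence it. Item 9 tests the calendar date of an AE against the date of first dose and never asks whether the event came before the infusion. Because of the recording rules in the protocol, a non-serious, non-procedural AE dated on the first dose date is expected to be a post-dose event.

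The risk is most plausible for acute terms. Item 9 draws hypertension from the Hypertension SMQ, diabetes from an SMQ that covers hyperglycaemia and new-onset diabetes, and chronic lung disease from the high-level term for bronchospasm and obstruction. Protocol 7.7 says of remdesivir infusion reactions: "Signs and symptoms may include hypotension, hypertension, tachycardia, bradycardia, hypoxia, fever, dyspnea, wheezing". The SAP's own list of hypersensitivity and infusion-related reaction terms (Appendix 2 item 36) includes hypertension, bronchospasm and bronchial obstruction. A participant with no such history who reacts to the first infusion could be reported with a treatment-emergent event and also appear as hypertensive, or as having chronic lung disease, at baseline.

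If that happened more often in one arm, subgroup membership would depend partly on treatment and the baseline table could show an imbalance that did not exist at randomization. SAP 3.3 and 3.4 let observed baseline imbalances prompt extra covariates in sensitivity analyses and extra subgroups, so the error could spread.

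**Working it through.** The point rests on date logic. The plan gives no figure here to reproduce.

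**Step 1: set the two definitions side by side** (factors other than current cancer).

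| AE start date | Baseline factor (item 9) | Treatment-emergent (7.1.5, item 8) | Both? |
|---|---|---|---|
| Complete, before first dose date | Yes | No | No |
| Complete, on first dose date | Yes | Yes | **Yes** |
| Complete, Day 2 or later | No | Yes, within the 30-day limit | No |
| Month and year only, same month as first dose | Yes | Yes, if the end date does not precede dosing | **Yes** |
| Year only, same year as first dose | Yes | Yes, if the end date does not precede dosing | **Yes** |
| Completely missing | Yes | Yes, if the end date is missing or does not precede dosing | **Yes** |

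For current cancer, only the second row is a clear overlap. Its rule for missing ongoing status admits some records on an incomplete end date without repeating the start-date condition, which is ambiguous.

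**Step 2: compare with the SAP's other baseline rules.** Table 3-1 ends the baseline window at the pre-dose point on Day 1. SAP 7.2.1 uses the date and time of first dose. Appendix 2 item 10 does not treat renal replacement therapy as baseline if it starts after the first dose date/time. Item 9 has no equivalent condition.

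**Step 3: how wide are the incomplete-date routes?** Take Days 2 to 29, which is 28 days. All lie inside the treatment-emergent window, because even a single dose on Day 1 plus 30 days reaches Day 31. Average over the 365 first-dose dates of a non-leap year, with onset assumed uniform over the 28 days. If r days remain in the month after first dose, min(r, 28) of the 28 days fall in the same month.

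- 31-day month: (0 + 1 + … + 28) + 28 + 28 = 406 + 56 = 462
- 30-day month: 406 + 28 = 434
- 28-day month: 0 + 1 + … + 27 = 378
- Month known: (7 × 462 + 4 × 434 + 378) / 365 = 5348 / 365 = 14.7 days, or 14.7 / 28 = 52%
- Year only: (406 + 28 × 336) / 365 = 9814 / 365 = 26.9 days, or 26.9 / 28 = 96%
- Date missing: 28 of 28 days

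These are shares of possible onset days given that the date is incomplete. They are not shares of AEs or of participants.

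**The case against.** The best defence is that few participants could change subgroup. AEs are reviewed daily in hospital (Protocol 6.4) and queries are resolved before the final analysis (SAP 2.3), so undated or partly dated AEs should be few. A Day 1 event changes a classification only if there is no matching medical history, and Protocol 1.1 describes a high burden of diabetes and hypertension in patients with chronic kidney disease. Laboratory abnormalities without clinical significance are not recorded as AEs (Protocol 7.6). The preferred-term lists were reviewed by medical monitors and are not shown, so the mapping of acute events is inferred from the source names. A site might also code such an event simply as an infusion-related reaction. Using AE records has a purpose too: a pre-dose SAE goes on the AE form and could otherwise be missed.

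All of this bears on size, and it stands. None of it removes the overlap, which is written into the rules.

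A reader might go further and infer any of the following. The documents do not support them:

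- *That post-dose AEs in general feed the subgroups.* A fully dated AE from Day 2 onward never qualifies.
- *That all seven factors are equally exposed.* The partial-date and missing-date rules are not written for current cancer, and the chronic liver disease search excludes transient and acute events.
- *That about half of post-dose events would be misclassified.* The 52% applies only to AEs with a missing day, and no count of these is given.
- *That a false imbalance between arms will result.* Protocol 7.7 lists reaction signs but gives no rates against saline.

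**Conclusion.** The concern holds, within limits. Item 9 allows an AE that began after the first dose to define a baseline risk factor by three routes: onset dated on the first dose date, a partial date in the month or year of first dose, or no start date. The last two apply to six of the seven factors. The same record can also be treatment-emergent, and nothing says which definition prevails.

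The subgroup analyses of the primary endpoint and mortality are affected, as is the between-arm baseline table. The alpha-controlled tests are not: SAP 3.3 and 6.1.3 stratify them by the three randomization factors only. It would be wrong to read this as a threat to the primary result.

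The number of participants affected cannot be computed from the documents and is probably small. The day counts of 14.7, 26.9 and 28 out of 28 are illustrative and assume uniform onset and first doses spread over a full year. The infusion-reaction example rests on the inferred mapping of terms. The correction is still worth making because it costs little.

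**What to change.** Amend SAP Appendix 2 item 9 as follows:

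- Derive baseline risk factors from medical history records.
- Add an AE record only when onset is documented before first dose. That means a complete start date before the first dose date, or a start on that date with a recorded pre-dose time or other documentation that it preceded dosing, such as a pre-dose SAE. The documents do not show whether AE onset time is collected, so the rule should not depend on a time field alone.
- Do not accept same-month, same-year or undated AE records unless an end date or other data shows that onset preceded dosing.
- Write the partial and missing start-date inclusion rules for medical history records. At present they appear only in the AE bullet, so deleting them there without restating them would leave medical history with no rule.
- Apply the pre-dose condition to current cancer as well, and make clear that its missing-ongoing-status rule is subject to it.

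The cost is a wording and programming change before unblinding. It needs no new data and does not alter sample size, alpha or power. If the SAP is already final, SAP 1 requires the change to be documented in the CSR. The downside is that a rare pre-dose SAE with an incomplete date and no other evidence of timing may not be counted.
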